A popular method of examining motivation involves an experimental paradigm known as effort-based decision-making, in which participants are asked to choose whether or not to invest physical effort in order to obtain an incentive or reward. Aversion to effort is a frequent and normal observation, both in animal and human experiments, in which the objective value of a reward is discounted by the effort costs and subjects opt to forgo physical effort at the expense of reward^{4,5}. This discounting can be defined mathematically by employing computational modelling to behavioural data and is seen to exhibit a concave or parabolic shape⁶. Previous studies of effort-based decision-making in both Parkinson's disease and schizophrenia have observed that individuals with these disorders experience greater amounts of effort discounting, which appears to be correlated with negative symptom burden and/or apathy^{7,8}. However it remains less well-known how individual's subjective experience of motivation symptoms relates to specific underpinning cognitive processes, such as integration of information about incentives (rewards) and costs such as effort, allocating attention or cognitive resources, or comparing value between different options. The current study would therefore aim to better understand these processes by examining decision-making in two clinical groups in which motivation problems are commonly reported and which are underpinned by dysregulation of dopamine-signalling - people with Parkinson's disease and people with early phase psychosis. The study would specifically investigate how the presence of multiple alternatives can affect decision-making by means of a novel behavioural task where participants either aim to minimise physical effort or maximise a reward – thereby allowing direct comparison between these different choice outcomes. Unlike previous experiments that have largely examined the willingness of participants to put in effort for an incentive, this experiment would more be concerned with the *dynamics* of these choices, employing well-established computational methods to better understand latent processes in these choices. In this way it will be possible to determine things like how physical effort influence decisions, potentially correlating with higher response caution observed in those with apathy, or alternatively apathetic individuals may display lower willingness to invest attention or cognitive resources regardless of the outcome.

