4.2. Outcome

Evidence-accumulation (computational) models will be fitted to behavioural data to further understand the dynamics of decision-making. It may be that certain apathy dimensions may correlate with specific computationally-derived parameters – for instance, the behavioural activation dimension may correlate with higher thresholds in effort-based task (greater caution), while the cognitive dimension may correspond to slower drift rates or lower response thresholds. These parameters may show dissociation in effort-avoiding and reward-maximising subtasks.

5. Design and methods of data collection and data analysis

Summary

The design will be a mixed quantitative/qualitative analysis. Quantitative data will be in the form of a computer-based decision-making task and questionnaire measures, primarily of apathy and negative symptoms. Qualitative data will take the form of semi-structured interview in a subset of participants.

Design

Those with or at high risk of psychosis will perform one in-person session, while those with Parkinson's disease will complete two counterbalanced sessions - once having taken their usual dopamine-modulating medication, and once having omitted this medication the same morning. These sessions will take place on separate days within 2 weeks of one another. If participants with Parkinson's disease feel unable to omit their medication, or do not take medication for Parkinson's disease, only a single session will be arranged. Testing will take place in person at the University of Birmingham.

At the point of recruitment, participants will receive a unique identifier. Pseudonymisation will be performed by [name] (JT). The database linking personal data to ID numbers will be maintained by JT in a single, password-encrypted Excel file on the University server. All datafiles generated will only refer to participants with their unique ID numbers.

[figure not shown]
Participants will receive a payment of £25 for participation in a session, plus up to £10 additional payment based on their performance in the task (i.e. up to £35 for a single session).

Behavioural study and questionnaires

(estimated time 1h 30 to 2h 5, depending on clinical group/session number)

- All participants will first receive a brief explanation of the study and provide written consent (~5 minutes).

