- Next all participants will complete the computerised decision-making task (~1h 15). In the task, participants will make choices using a computer keyboard, in which the outcome is either physical effort, delivered via a handheld dynamometer (SS25LA, BIOPAC Systems), or a gain or loss of reward credits (that corresponds to an additional bonus payment at the end of the experiment), requiring no physical effort. Reward and effort subsections will be counterbalanced. Data from computer-based tasks (outcomes include reaction times, choice, subjective rating of decision difficulty, force metrics) will be saved as a datafile at the end of the experiment.
- Next participants will complete a set of questionnaires (35 minutes for participants with early psychosis, 40 minutes for people with Parkinson's disease attending their first session; if people with Parkinson's disease are attending for their second session, they will only be required to complete part III of the UPDRS score (a motor exam of ~ 5 minutes duration) and digit span test. Questionnaire data will be collected using the University-approved online survey software Qualtrics or using pen and paper (any paper records will not contain personal information and will be stored in locked filing cabinets within the Centre for Human Brain Health).

The questionnaire battery to be completed by all participants includes:

- -Apathy Motivation Index (~3 minutes)
- -Dimensional apathy scale (~3 minutes)
- -Snaith-Hamilton Pleasure Index (~ 2 minutes)
- -Adapted Glasgow Content of Thought Inventory (~2 minutes)
- -Patient Health-Questionnaire-8 (~2 minutes)
- -Fatigue Severity Scale (~2 minutes)
- -Montreal cognitive assessment (~5 minutes)
- -Forward and backward digit span test (~2 minutes)

All above questionnaires are validated, with the exception of the Glasgow Content of Thoughts Inventory, which is an abbreviated version of an existing, validated questionnaire for insomnia, which has been repurposed to quantify spontaneous cognitive activity/thought.

In addition to the above questionnaires, people with Parkinson's disease attending their first session will complete the validated semi-structured interview questionnaire:

-Unified Parkinson's disease rating scale (~20 minutes)

In addition to the above questionnaires, people with early psychosis will complete the validated semistructured interview questionnaire:

-Brief Negative Symptom Scale (BNSS) (~15 minutes)

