Quantitative data will be analysed using descriptive statistics (such as mean, median), and linear mixed effect models using reaction time and accuracy as dependent variables and questionnaire scores as predictive regressors, using statistical software such as R and Python. Evidence accumulation (drift diffusion) models will be fitted to participant data (using tools such as HDM or DMC including for Bayesian model comparison), and computationally derived parameters (e.g. for drift rate, threshold) will be analysed in linear mixed effect models with questionnaire scores as regressors. Qualitative data from interview will be analysed with interpretative phenomenological analysis by JT, with support and advice by MB.

6. Project setting

All participants attending in person will conduct the experiment in testing rooms at the School of Psychology, [name] where MAJA has dedicated laboratories containing necessary equipment for the experiment. All testing rooms are accessible by lift. Any necessary provisions, including drinks, snacks and walking aids will be provided to participants.

7. Participant recruitment

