10.1. Assessment and management of risk

See section 13.4 in the protocol for further information on risks. The following describes the main potential risks of the study:

Questionnaires:

Questionnaires enquire about or probe symptoms such as cognition, mood, fatigue and apathy and the impact on activities of daily living, which might cause a degree of emotional distress during completion but overall these risks are deemed to be low. In general, the included questionnaires do not contain highly sensitive or probing questions. The PHQ-8, which quantifies symptoms of depression, omits a question that asks about 'thoughts that you would be better off dead, or of hurting yourself in some way' posed in the longer PHQ-9 questionnaire, and therefore is less likely to raise safeguarding issues. The UPDRS (administered to participants with Parkinson's disease to assess different motor and non-motor symptoms) and BNSS (administered to participants with early psychosis to assess negative symptoms) are administered via a semi-structured interview but overall do not include highly sensitive or probing questions and are unlikely to cause distress.

Experimental tasks:

The effort-based task requires participants to squeeze a handheld force-meter on repeated occasions throughout the experiment (total 160 trials). Participants with pre-existing injuries or musculoskeletal problems will be screened for and excluded at the outset. As the experiment aims to examine decisions involving physical effort, participants are likely to experience some degree of exertion-related discomfort during the experiment. However a very large number of studies have employed these methods, including in people with Parkinsons' disease and psychosis 19,20 without significant problems or adverse events. Maximum grip force is measured at the beginning of the experiment to ensure that all work tasks are calibrated to individual participants, with no tasks exceeding 80% of the maximum calibrated force, whilst the nature of the experiment encourages participants to select lower effort options most frequently. Rest blocks are interposed every 20 trials to ensure adequate rest and recovery. If participants experience significant discomfort and indicate they wish to terminate the experiment, the experiment will be terminated immediately.

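### The effort and reward subsections are counterbalanced, but the analysis text names no subsection-order term, which may cost precision in the effort-versus-reward comparison and the apathy-by-subtask test

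*Protocol*

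**What the plan says.** All quotations are from the Protocol.

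- **Design.** Section 5, Behavioural study and questionnaires: each session contains one computerised task of about 75 minutes with an effort part and a reward part. "Reward and effort subsections will be counterbalanced". The scheme (per person, per session or by block) is not described.
- **Analysis.** Section 5, Data analysis, describes "linear mixed effect models using reaction time and accuracy as dependent variables and questionnaire scores as predictive regressors". The drift-diffusion parameters "will be analysed in linear mixed effect models with questionnaire scores as regressors". No subsection-order, period or trial-number term appears anywhere in the protocol.
- **Use of the two parts.** The Background says that participants either minimise effort or maximise reward, "thereby allowing direct comparison between these different choice outcomes". Section 4.2 links the behavioural activation dimension of apathy to the threshold in the effort task, and adds: "These parameters may show dissociation in effort-avoiding and reward-maximising subtasks".
- **Fatigue control.** Section 10.1: "Rest blocks are interposed every 20 trials to ensure adequate rest and recovery".

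**The concern.** Whichever part comes second is done with more practice and more fatigue. Counterbalancing makes that shift cancel from the group-average difference between effort and reward. It does not cancel within a person: effort-first participants carry the shift with one sign and reward-first participants with the other. A model without order treats this known, assigned variation as residual error.

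That matters for any analysis built on each person's effort-minus-reward difference. Two such analyses are foreseen: the direct comparison in the Background and the dissociation by subtask in section 4.2. The issue is separate from the on/off medication order, because it also applies to the psychosis group, who attend once.

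**Working it through.** **The protocol's own figures (section 7.2.1).** 82 × 180/160 = 92.25, which agrees with the stated 92. 50 × 160/4 = 2,000 observations per condition, above the required 1,600. Both reproduce and neither is in dispute. The four conditions counted there are option number by difficulty; effort versus reward and its order are not among them.

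**Inputs.** N = 100 per group (section 7.2.1). Assumed, because the protocol does not give them: two-sided 5% level, 80% power with an order term in the model, one order per person per session with half in each order, an additive order effect and no carry-over.

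**Set-up.** Let p be the shift from first to second subsection.

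- Effort minus reward: δ − p + e for effort-first people and δ + p + e for reward-first people. Without an order term the variance is multiplied by 1 + r², where r = p/SD of the difference.
- Score in one subsection: shifted by half of p either way about its mean. The multiplier is 1 + r²/4, with r now p/between-person SD.
- Average of both subsections: everyone has one first and one second part, so p/2 is a constant. The multiplier is 1.

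**Power without the term.** Φ(2.802/√multiplier − 1.960), where 2.802 = 1.960 + 0.842. Example at r = 0.5: 2.802/√1.25 − 1.960 = 0.546, and Φ(0.546) = 70.7%.

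| r | Multiplier, difference | Power, difference | Equivalent N (of 100) | Power, one subsection | Power, average |
|---|---|---|---|---|---|
| 0.1 | 1.01 | 79.6% | 99 | 79.9% | 80% |
| 0.25 | 1.0625 | 77.6% | 94 | 79.4% | 80% |
| 0.5 | 1.25 | 70.7% | 80 | 77.6% | 80% |
| 1.0 | 2.00 | 50.8% | 50 | 70.7% | 80% |

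The difference columns apply directly to the slope of the difference score on apathy, which is the apathy-by-subtask test. For the group-mean contrast with exactly equal numbers in each order, the estimate itself is undisturbed and only its standard error is too large. Power is then Φ(2.802 − 1.960√(1 + r²)), which is 78.3%, 72.9% and 51.2% at r = 0.25, 0.5 and 1.0. The mean contrast therefore loses about 2, 7 and 29 points instead of 2, 9 and 29.

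**Simulation check** (N = 100, 4,000 runs, equal numbers in each order). Here p is in between-person SD per subsection and the SD of the difference is 0.85, so p = 0.5 is 0.5/0.85 = 0.59 SD of the difference. Each cell gives power with order omitted, then included.

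| p | Effort-reward mean | Apathy within effort | Apathy, average of both |
|---|---|---|---|
| 0.25 | 76.3% v 78.8% | 75.8% v 76.4% | 84.1% v 83.7% |
| 0.5 | 68.4% v 79.0% | 74.8% v 77.0% | 85.1% v 84.7% |
| 1.0 | 38.5% v 79.5% | 67.5% v 76.8% | 84.2% v 84.0% |

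The pattern matches the algebra: the loss is largest for the difference, smaller within one subsection and absent for the average.

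**The case against.** Three points count against this concern.

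**The text is a summary.** The Data analysis paragraph does not say that questionnaire scores are the sole regressors. It also leaves out option number, difficulty, effort versus reward, medication state and random effects, all of which the aims need. A reader might infer that the models formally exclude everything but questionnaire scores. The documents do not support that, and read that way there would be no effort-versus-reward term to weaken. A full list of model terms is commonly left to a statistical analysis plan, which is not shown here. This stands: the protocol contains no error or contradiction on the point. What remains is that section 5 names regressors but not the order factor that the same section builds into the design.

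**The counterbalancing scheme is not described.** If effort and reward blocks alternated within a session, little or none of the shift would survive in each person's difference. Swapping the order between a Parkinson's participant's two sessions would have a similar effect on results averaged over both. This stands as an assumption behind every figure above.

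**The size is unknown and may be small.** Rest breaks limit fatigue, though not practice. At 0.25 SD of the difference or less, the loss is only 2 to 3 points. This also stands and sets the priority.

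A reader might also infer that the main apathy association loses power, or that results would be biased. Neither follows. Apathy slopes averaged over both subsections lose nothing under an additive effect, and counterbalancing already removes the expected bias.

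**Conclusion.** The concern holds as a low-priority precision point. If order is fixed per person or per session, leaving it out of the model costs power where the two subtasks are contrasted. From an assumed 80%, the loss is about 2 to 3 points at 0.25 SD of the difference, about 9 at 0.5 SD (about 7 for a mean contrast with exactly equal orders) and about 29 at 1.0 SD. Within one subsection the same multiples of the between-person SD cost about 1, 2 and 9 points. For apathy averaged over both subsections the loss is nil. Whether it matters in practice depends on an order effect that the protocol does not quantify; it becomes material from about 0.4 to 0.5 SD of the difference.

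**What to change.** In section 5, Data analysis, state that models of subtask-specific outcomes and of effort-reward contrasts include subsection order (effort first or reward first, coded for each session) and its interaction with subtask as fixed effects, with the apathy terms unchanged. In a model holding both subtasks, the interaction is the term that absorbs the practice or fatigue shift. In a model of a difference score or a single subtask, order alone does so.

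It would help to say in the same place how the subsections are counterbalanced. If the healthy-adult pilot of more than 60 people (section 3) ran both subsections, it could show how large the order effect is.

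The cost is a sentence or two and one or two degrees of freedom out of about 100 participants per group. Order is set by the design and can be recorded at each session, so no extra participants or assessments are needed.

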This study aims to better understand motivation problems in those with Parkinson's disease and early psychosis (clinical high risk/first episode). We know that motivation impairments are common in these conditions, but for most individuals negative symptoms tend to be simplistically grouped into categories of 'diminished expression' and 'motivation and pleasure'. However, in reality the neuroscience of motivation is complex, with much recent research demonstrating that specific areas of the brain are important in different aspects of decision-making, such as preferentially encoding rewards vs costs¹²,translating incentives onto a common scale of value¹³, controlling and allocating cognitive resources/attention¹⁴, and converting decisions to an appropriate action¹⁵. Despite increased understanding of these processes, we remain unable to correlate someone's individual apathy symptoms with dysfunction at the level of the underlying cognitive processes such as described above.

This study builds on previous experiments using effort- and reward-based decision-making, as well as clinical reports of patients experiencing difficulty in decisions encompassing multiple alternatives. It will examine devaluation of rewards by effort (a hallmark of apathy), whilst also studying effects of multiple alternatives on decision-making. It will also aim to examine specifics effects of dopamine on decision-making, by testing Parkinson's disease patients on and off their usual dopaminergic medication in counterbalanced sessions. Modern computational techniques will be applied to the data to better understand how different parameters affect decision-making in the participants. The research will also aim to examine the subjective experience of apathy in much greater detail than most existing studies, in order to better inform the quantitative analysis.

A proof-of-concept study has already been conducted in healthy adults (under ERN 18-1800E and ERN 20-1897PA). This confirms that the experiment captures expected behaviour (slower and less accurate responding in conjunction with closer-value choices and choices involving more options), with all (n > 60) participants managing to complete the experiment without problems.

4. Research question/aims

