7.2. Sampling

7.2.1. Size of sample

Around 100 participants with Parkinson's disease, and around 100 participants with or at high risk of developing psychosis will be recruited. As there are no existing studies employing the same or similar task, sample sizes have been estimated based on previous related work. A previous analysis¹⁷ by Brysbaert and colleagues estimated that a properly powered reaction time experiment with repeated measures analysed with linear mixed effect models should have at least 1,600 observations per condition (e.g., 40 participants, 40 stimuli), which assumes an effect size between Cohen's d = 0.4 and d = 0.5. Given the experiment contains a total of four experimental conditions (two vs three options, easy vs difficult choice difficulty), 50 participants performing 160 trials would be sufficiently-powered. Another study by Saleh et al.¹⁹ analysed reaction time data and fitted a drift diffusion model to 82 participants with cerebral small vessel disease performing an effort-based decision-making task, including those suffering with apathy. They found a significant correlation between computationally-derived parameters and apathy scores, suggesting that their study of 82 participants performing 180 trials was sufficiently powered. Accounting for a smaller number of (160) trials, 92 participants would be necessary to achieve a similarly-powered study.

For the interview-based study, an estimated sample size of ~10 individuals (~5 with Parkinson's disease and 5 with or at high risk or psychosis) should enable a diverse range of insight while balancing feasibility.

7.2.2. Sampling technique

Convenience sampling will be employed. As all participants will perform the same experiment, there is no rationale for randomisation or group allocation. For the interview-based study, judgement sampling on the basis of performance in the first experiment will guide participant selection. As the experiment principally aims to investigate motivation symptoms, participants with high levels of apathy or negative symptoms, particularly those with exaggerated distractor effects or effort-discounting on the behavioural task, will be preferentially selected for interview.

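### Accuracy is right or wrong on each trial but is assigned a linear mixed model, which can show apathy-by-condition interactions that only reflect compression near ceiling

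*Protocol*

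**What the plan says.** The Data analysis part of protocol Section 5 plans "linear mixed effect models using reaction time and accuracy as dependent variables", with questionnaire scores as the predictors. Reaction time and accuracy therefore share one model type. No logistic model, link function or transformation for accuracy appears anywhere in the protocol. The same paragraph plans drift-diffusion models, whose parameters are then regressed on questionnaire scores.

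Other parts of the protocol bear on this:

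- The Project summary (Procedure) lists accuracy among the primary data.
- Section 7.2.1 gives four conditions, "two vs three options, easy vs difficult choice difficulty".
- Section 3 says the pilot in healthy adults showed "slower and less accurate responding in conjunction with closer-value choices and choices involving more options". It gives the direction but no accuracy rates.
- Section 4.1 asks how apathy relates to valuing options among several alternatives and to allocating cognitive resources as choice difficulty varies.

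**The concern.** On the probability scale, cells near 100% correct have little room to move. An apathy effect of the same log-odds size everywhere then appears small in easy trials and larger in hard ones. A linear model reads that difference as an apathy-by-difficulty interaction. The same can happen for two against three options.

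The objectives in Section 4.1 make these interactions natural tests, although the Data analysis text does not write them out. A general reduction in accuracy could then be reported as a deficit specific to difficult or multi-option choices, which is the kind of dissociation the study looks for.

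**Working it through.** **The plan's own figures.** 160 trials / 4 conditions = 40 trials per condition. The cited benchmark of 1,600 observations per condition needs 1,600/40 = 40 participants, and 50 participants give 50 × 40 = 2,000. Scaling the reference study gives 82 × 180/160 = 92.25, the stated 92. These figures reproduce. The benchmark concerns reaction time ("which assumes an effect size between Cohen's d = 0.4 and d = 0.5"), so it neither supports nor undermines the accuracy analysis.

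**Compression by hand.** A drop of 0.2 log-odds multiplies the odds by exp(−0.2) = 0.819.

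| Starting accuracy | Odds | Odds after | Accuracy after | Drop (points) |
|---|---|---|---|---|
| 95% | 19 | 15.56 | 94.0% | 1.0 |
| 90% | 9 | 7.37 | 88.0% | 2.0 |
| 75% | 3 | 2.46 | 71.1% | 3.9 |
| 60% | 1.5 | 1.23 | 55.1% | 4.9 |

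The same effect costs 1.0 point at 95% and 3.9 at 75%, a gap of 2.9 points per SD of apathy. At 75% and 60% the gap is about 1 point.

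**Two-level simulation.** Assumed inputs: 100 participants, 40 trials per level, random-intercept SD 0.5 on the logit scale, no interaction on the logit scale, two-sided 5% test. The linear test regresses each participant's easy-minus-hard proportion on apathy. Ranges cover repeated runs.

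- At 95%/75%, effects of 0.1, 0.2 and 0.3 log-odds per SD: the linear test rejects in 22-25%, 70-73% and 96% of runs, the logit model in 6-8%. With 80 trials per level the linear rates are 33%, 85% and 99%.
- At an effect of 0.2, linear rejection is 47% at 90%/75%, 40% at 85%/65% and 12-16% at 75%/60%.

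**Full 2 × 2 simulation.** Assumed inputs: 100 participants, 40 trials per cell, random-intercept SD 0.6, additive log-odds effects only, no guessing floor, 400 runs per setting (Monte Carlo error about 2 points). Entries are linear-model rejection rates with by-participant slopes, as apathy-by-difficulty / apathy-by-options.

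| Accuracy: easy-2, easy-3, difficult-2, difficult-3 | No apathy effect | −0.2 per SD | −0.4 per SD |
|---|---|---|---|
| 0.97, 0.94, 0.84, 0.73 | 5% / 5% | 74% / 27% | 100% / 79% |
| 0.95, 0.91, 0.81, 0.70 | 5% / 5% | 72% / 28% | 99.8% / 72% |
| 0.90, 0.85, 0.73, 0.62 | 7% / 5% | 55% / 17% | 98.5% / 48% |
| 0.80, 0.73, 0.64, 0.55 | 8% / 4% | 18% / 10% | 58% / 20% |
| 0.70, 0.61, 0.51, 0.41 | 6% / 5% | 7.5% / 5% | 10% / 6% |

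A random-intercept binomial-logit mixed model stays at 2.5-7.5% in every setting. A linear model with random intercepts only (approximated here) rejects apathy-by-difficulty in 17-27% of runs even with no apathy effect, when easy two-option accuracy is 0.90-0.97.

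**The reverse case.** In an unbiased two-choice diffusion model the log-odds of a correct choice are proportional to threshold × drift. A uniform 10% cut in threshold therefore takes 10% off each log-odds: 0.29 off 2.94 (95%) and 0.11 off 1.10 (75%). The log-odds changes differ, while the accuracy drops are closer, 1.6 and 2.1 points (95% to 93.4%, 75% to 72.9%). Simulated at 95%/75%, 100 participants and 40 trials per level, with assumed person SD 0.2 in log threshold for the threshold case:

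| Uniform apathy effect per SD | Linear rejects | Logit rejects |
|---|---|---|
| Log threshold 0.05 | 7% | 19% |
| Log threshold 0.10 | 12% | 44% |
| Log threshold 0.15 | 19% | 80% |
| Log threshold 0.20 | 38% | 94% |
| Lapse log-odds 0.3 | 7% | 33% |
| Lapse log-odds 0.5 | 14% | 66% |

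A repeat agreed in direction: 12% against 48% for threshold, 15% against 70% for lapse.

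**The case against.** The strongest objection is that the logit scale is not privileged here. Section 4.2 expects apathy to act on thresholds as well as drift rates, and Section 1 raises lower willingness to invest attention. If apathy acts uniformly on threshold or on lapses, the logit model shows more interactions than the linear one. The low logit rates in the first two simulations follow from generating data with no logit-scale interaction. This stands. A reader might infer that testing interactions on the logit scale settles the matter because it is the scale of the choice process; the protocol's own process model does not support that.

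Three further objections hold in part:

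- The plan already has a process-level analysis. Section 4.2 names only the model parameters as outcomes, so the accuracy regressions sit beside them. They would still be reported, and accuracy is listed as primary data.
- The interaction terms are implied by Section 4.1, and main effects would also answer part of the question.
- Model details are often left to a statistical analysis plan, which is not at hand. Here, however, the protocol names the model.

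**Conclusion.** The linear model for accuracy is a poor choice as written and should be replaced; severity is moderate. The size depends on two assumptions: easy-condition accuracy of roughly 80% or more, and some overall apathy effect on accuracy. The second is the study's own hypothesis; the first cannot be checked, because no accuracy rates are given. At 0.2 log-odds per SD, linear rejection of apathy-by-difficulty runs from about 70% at 95%/75% to about 15% at 75%/60%. Apathy-by-options is weaker, at most 28% for that effect. With no apathy effect, the linear model with by-participant slopes stays near nominal.

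A reader might infer that the linear model will produce false interactions. The documents support only that it can. Such differences are real in percentage points and spurious only relative to an additive log-odds effect. Nor does this point show that the reaction-time model is wrong: nothing here bears on it or on the drift-diffusion analyses.

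**What to change.** Amend the Data analysis text in Section 5 so that:

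- trial-level accuracy is analysed with a binomial (logistic) mixed model with participant random intercepts and by-participant slopes for difficulty and number of options, reporting predicted probabilities by condition alongside the odds ratios;
- an apathy-by-condition interaction in accuracy, on either scale, is not read as process-specific unless the planned drift-diffusion parameters support it. Chance accuracy presumably differs between two options (1/2) and three (1/3), so a plain logit may not fully neutralise that comparison.

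Leave the reaction-time model as it is. The change needs no new data or participants, and the named software (R, Python) can fit the model. The cost is about one sentence for the model and one for interpretation; coefficients become odds ratios, which the predicted probabilities help readers follow.
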